3.1. FRAMEWORK

All quantitative variables, including those based on calculations (secondary elements), will be analyzed with a case summary evaluation before the detailed characteristics and parameters can be evaluated. A case summary contains a listing of the number of valid cases/values, missing cases/values (if any) and total cases/values in the specific analysis. In general, as central position parameter for quantitative variables the mean, median and mode will be analyzed. As variation parameter the standard deviation, 95% confidence interval of the mean, interquartile range and range (based on maximum and minimum) will be calculated. All quantitative variables will be assessed for normality using the Shapiro-Wilk test. For optional visualization of quantitative variables, box-and-whisker plots will be used. Additional analyses like skewness and kurtosis measures or standard errors are also optional.

All qualitative variables, including those based on summaries (secondary elements), will be analyzed listing the proportions, frequencies, column and row totals, and missing proportion (if any).

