3.1.1. Primary Analysis / Endpoint

The objective of the clinical investigation is to demonstrate the non-inferiority (equal or better) of the ASES Shoulder Score in relationship to the officially cleared indications in comparison to respective clinical outcome data in the scientific literature.

Data collection of ASES Shoulder Score will be collected according to the schedule in Table 1, Schedule of Events. This will be repeated annually in all subjects who have the prosthesis with

full or partial implant survival (including all subjects without removal of all endo-prosthesis components).

The 24 months postoperative results for subjects implanted with ReUnion RFX System will be compared to a historical group and results reported by respective clinical outcome data in the scientific literature.

Higher ASES Shoulder Score results are linked to better subject results and vice versa.

The clinical investigation endpoint is non-inferiority to the control, meaning the clinical investigation result should be equal or better than the control. In this clinical investigation, an equal or better ASES Shoulder Score result means equal or more (\geq). As only results from samples will be captured, results are mostly estimates of the true population parameter. These estimates vary by a certain area, where it is expected that the true population parameter falls within. Based on this, it is required to specify a lower limit for the acceptable difference or zone of indifference, denoted as $-\theta$.

Hypotheses are developed to allow for a comparison of the 24 months postoperative ASES Shoulder Score effectiveness/performance between the two underlying populations. The 24 months post-operative ASES Shoulder Score is the primary endpoint of this clinical investigation. Hypothesis tests will be one-sided with a significance level α of 5%.

Arm A (TSA/HA)		
Hypothesis	Equations	Interpretation
Null (H_0)	$A - B < -\theta$	Central tendency of A is inferior to the central tendency of B.
	ReUnion RFX System (TSA/HA) – Control (Benchmark) $< -\theta$	
Alternative (H_1)	$A - B \geq -\theta$	Central tendency of A is non-inferior to the central tendency of B.
	ReUnion RFX System (TSA/HA) – Control (Benchmark) $\geq -\theta$	
Possible Evidence (p)	Possible Decisions	Possible Conclusions – ASES score

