$p\text{-value} > \alpha (0.05)$	Fail to reject null hypothesis (H_0)	ReUnion RFX System (TSA/HA) $<$ Control (Benchmark) Insufficient evidence to reject the null hypothesis ($H_0: A - B < -\theta$) at the pre-determined significance level of 5%.
$p\text{-value} \leq \alpha (0.05)$	Reject null hypothesis (H_1)	ReUnion RFX System (TSA/HA) \geq Control (Benchmark)

		Sufficient evidence to reject the null hypothesis ($H_0: A - B < -\theta$) at the pre-determined significance level of 5%.
--	--	--

Table 3.1.1.1: Arm A (TSA/HA)

The primary objective of the clinical investigation is to demonstrate non-inferiority of the ASES Shoulder Score at 24 months post-operative compared to the benchmark literature for Arm A. The 24 months mean ASES Shoulder Score result of the RFX System (TSA/HA) will be compared to the pooled postoperative mean estimate of the control group (58.74 points). The pooled standard deviation of the post-operative ASES Shoulder Score result of the benchmark (20.33 points) was used to determine lower limit. The lower maximum acceptable difference ($-\theta$) is 38.41 points (mean of control $-\theta$ or $58.74 - 20.33 = 38.41$ points).

Based on the underlying distribution of the data and the result of the normality assessment, either the parametric one-sample t-test or the non-parametric one-sample sign test will be used to compare the 24 months postoperative ASES Shoulder Score results of the ReUnion RFX System (TSA/HA) against the value of 38.41 points.

Arm B (RSA)		
Hypothesis	Equations	Interpretation
Null (H_0)	$A - B < -\theta$	Central tendency of A is inferior to the central tendency of B.
	ReUnion RFX System (RSA) – Control (Benchmark) $< -\theta$	
Alternative (H_1)	$A - B \geq -\theta$	Central tendency of A is non-inferior to the central tendency of B.
	ReUnion RFX System (RSA) – Control (Benchmark) $\geq -\theta$	
Possible Evidence (p)	Possible Decisions	Possible Conclusions – ASES score
p-value $> \alpha$ (0.05)	Fail to reject null hypothesis (H_0)	ReUnion RFX System (RSA) $<$ Control (Benchmark) Insufficient evidence to reject the null hypothesis ($H_0: A - B < -\theta$) at the pre-determined significance level of 5%.
p-value $\leq \alpha$ (0.05)	Reject null hypothesis (H_1)	ReUnion RFX System (RSA) \geq Control (Benchmark) Sufficient evidence to reject the null hypothesis ($H_0: A - B < -\theta$) at the pre-determined significance level of 5%.

Table 3.1.1.2: Arm B (RSA)

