The primary objective of the clinical investigation is to demonstrate non-inferiority of the ASES score at 24 months post-operative compared to the benchmark literature for Arm B. The 24 months mean ASES Shoulder Score result of the RFX System (RSA) will be compared to the pooled postoperative mean estimate of the control group (74.48 points). The pooled standard deviation of the post-operative ASES Shoulder Score result of the benchmark (11.08 points) was used to determine the lower limit. The lower maximum acceptable difference ($-\theta$) is 63.40 points (mean of control - θ or $74.48 - 11.08 = 63.40$ points).

Based on the underlying distribution of the data and the result of the normality assessment, either the parametric one-sample t-test or the non-parametric one-sample sign test will be used to compare the 24 months postoperative ASES Shoulder Score results of the ReUnion RFX System (RSA) against the value of 63.40 points.

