4.7. CONFIDENCE INTERVALS AND P-VALUES

The following acceptance / rejection criteria were used for this clinical investigation:

Parameter	Acceptance / rejection criteria
Confidence level (1- α)	0.95 (95%)
Significance level (α)	0.05 (5%)
Power (1- β)	0.80 (80%)
Beta-level (β)	0.20 (20%)
Confidence interval of mean	95%
p-value indicating significance	≤ 0.05

Table 4.7: Acceptance / Rejection Criteria

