4.10. ASSUMPTIONS

In case of deviation from assumptions (e.g. normality), non-parametric methods will be used for analysis. No transformation of such data will be performed.

5. Population and Progress

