6.6. ANALYSIS OF CI ENDPOINTS

Evaluation Variable / Question	Level of Measurement	Analysis Plan	Inclusion		
Endpoints – Primary Endpoint Arm A (TSA/HA)			IR	FR	N/A
Use variable Total ASES Score 24 Months [points]:					
Based on the underlying distribution of the data and the result of the normality assessment, either the parametric one-sample t-test or the non-parametric one-sample sign test will be used to compare the 24 months postoperative ASES Shoulder Score results of the ReUnion RFX System (TSA/HA) against the value of 38.41 points.				X	
The analysis of the primary endpoint will be part of the final report					
Endpoints – Primary Endpoint Arm B (RSA)			IR	FR	N/A
Use variable Total ASES Score 24 Months [points]:					
Based on the underlying distribution of the data and the result of the normality assessment, either the parametric one-sample t-test or the non-parametric one-sample sign test will be used to compare the 24 months postoperative ASES Shoulder Score results of the ReUnion RFX System (RSA) against the value of 63.40 points.				X	
The analysis of the primary endpoint will be part of the final report.					

Table 6.6.1: Endpoints – Primary Endpoint Tables List

Evaluation Variable / Question	Level of Measurement	Recode and Analysis Plan	Inclusion		
			IR	FR	N/A
Adverse Events – Time to (earliest) Device Related Adverse Event / Incident					
Creation of variable Difference between Date of Surgery [dd.mm.yyyy] and Date of First Device Related Adverse Event [dd.mm.yyyy] in days  (Variable(s): VISITDT; AEONSTDT)	Quantitative, ratio	Case summary with number and percentage of valid cases/values, missing cases/values (if any) and total cases/values. Mean, median, interquartile range, maximum, minimum, standard deviation, 95% confidence interval for mean, Shapiro-Wilk Test.		X	
Creation of variable Difference between Date of Surgery [dd.mm.yyyy] and Date of “most recent” Visit [dd.mm.yyyy] in days  (Variable(s): VISITDT)	Quantitative, ratio	N/A (Analyzed above), used for survivorship		X	
Create new variable “Grouping variable – First Device Related Adverse Event” (Variable(s): AEONSTDT)	Qualitative, nominal	- censored = survivors - events = first (earliest) Device Related Adverse Event		X	

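### A normality pre-test can move the primary test from the mean to the median against the same mean-based constant; any rise in false non-inferiority depends on left skew and arm size

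*SAP*

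**What the plan says.** SAP 3.1.1 words the objective as a comparison of means in both arms: "The 24 months mean ASES Shoulder Score result of the RFX System (TSA/HA) will be compared to the pooled postoperative mean estimate" and "The 24 months mean ASES Shoulder Score result of the RFX System (RSA) will be compared to the pooled postoperative mean estimate". The tested constants are 58.74 - 20.33 = 38.41 (Arm A) and 74.48 - 11.08 = 63.40 (Arm B). The power statements in SAP 3.2.1 and 3.2.2 are also for a mean with a given SD.

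Three other SAP passages determine which test is used:

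- Section 3.1: "All quantitative variables will be assessed for normality using the Shapiro-Wilk test".
- Section 4.10: "In case of deviation from assumptions (e.g. normality), non-parametric methods will be used for analysis", and data are not transformed.
- Section 6.6: "either the parametric one-sample t-test or the non-parametric one-sample sign test will be used to compare the 24 months postoperative ASES Shoulder Score results", against the same constant in either case.

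Protocol 8.1, 8.2 and 11.3.2 repeat the choice of test. The hypothesis tables do not name a parameter: "Central tendency of A is inferior to the central tendency of B". The level is set by "Hypothesis tests will be one-sided with a significance level" of 5%. No cut-off for the normality check is given. The value 0.05 is inferred from SAP 4.7, where it is the "p-value indicating significance".

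**The concern.** A one-sample sign test asks whether more than half of subjects score above the constant. It takes no account of how far below it the others fall, so it tests the median. Neither document gives a median benchmark. If normality is rejected, the claim therefore rests on a different parameter, chosen by the trial's own data and held against a constant built for the mean.

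With left-skewed scores the median lies above the mean. An arm whose true mean sits exactly on the threshold then has more than half its subjects above it, and the sign test can declare non-inferiority too often for a claim about the mean. It can even do so when the observed mean is below the constant. A one-sided t-test cannot, because its statistic is then negative.

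**Working it through.** **The plan's own figure.** The effect size is (74.48 - 63.40)/11.08 = 1.0, and likewise 20.33/20.33 = 1.0 in Arm A. A one-sample t-test with n=10 and two-sided 5% has noncentral-t power of 80.3%, which matches the documents. At one-sided 5% it is 89.8%.

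**The sign test alone at n=10, normal data.** P(score > constant) = Φ(1) = 0.841. The critical count is 9 of 10 (actual size 0.011), and P(Bin(10, 0.841) ≥ 9) = 0.513. So 80.3% does not describe the sign-test branch.

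**False non-inferiority under the rule.** The method was simulation with 20,000 samples per cell and the true mean set on the constant. If Shapiro-Wilk p ≤ 0.05, an exact sign test is used, otherwise a t-test, at one-sided 5%.

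Assumed, because the documents do not say:

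- Scores run from 0 to 100, and the Shapiro-Wilk cut-off is 0.05.
- Evaluable numbers per arm, since no split of the 100 is fixed: 10 (the powered size); 22 = 50 × 0.44; 32 = half of 100/1.56; 50 (equal split, no loss); 44 = 100 × 0.44 (everyone in one arm, an extreme).

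Shapes for Arm B, mean 63.40:

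- Beta, with k = m(1-m)/s² - 1, a = mk, b = (1-m)k and m = 0.634. For s = 0.1108: k = 0.2320/0.01228 - 1 = 17.9. For s = 0.254, the largest Arm B source SD: k = 0.2320/0.06452 - 1 = 2.60.
- Illustrative mixtures, not from the documents: a share p of poor outcomes distributed N(29, 12), the rest with SD 8 and mean (63.40 - 29p)/(1-p), which is 65.2, 67.2 and 72.0 for p = 5, 10 and 20%.

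Results, rule vs t-test always (%):

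| Arm B shape | P(score > 63.40) | n=10 | n=22 | n=44 |
|---|---|---|---|---|
| Beta, SD 11.08 | 0.518 | 5.6 vs 5.7 | 5.7 vs 5.4 | 6.4 vs 5.4 |
| Beta, SD 25.4 | 0.547 | 6.4 vs 7.2 | 7.6 vs 6.2 | 15.4 vs 6.2 |
| Mixture 5% | 0.559 | 9.8 vs 9.9 | 12.7 vs 9.6 | 20.6 vs 8.7 |
| Mixture 10% | 0.615 | 15.0 vs 14.3 | 22.1 vs 10.8 | 45.2 vs 8.8 |
| Mixture 20% | 0.687 | about 18 vs 13 | 44 vs 9 | 81 vs 7 |

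For beta SD 25.4 the other sizes give 7.9 vs 5.9 (n=32) and 11.8 vs 5.8 (n=50). The rise is not monotone because the sign test is discrete: the critical counts are 16/22 (size 0.026), 22/32 (0.025), 28/44 (0.048) and 32/50 (0.032). Repeat runs agree within simulation error.

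A different left-skewed family (reflected gamma) gives 8.8 vs 8.8 (skew -1) and 12.4 vs 13.1 (skew -2) at n=10. At n=12, skew -2, it gives 15.9 vs 12.8. The excess therefore starts just above the powered size.

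**Arm A, right-skewed beta, mean 38.41, n=44.** SD 20.33: 4.2 vs 4.5. SD 31.0: 1.1 vs 4.3. No inflation.

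**Is left skew plausible in Arm B?** In the source with mean 69.3 and SD 25.4, a ceiling of 100 lies (100 - 69.3)/25.4 = 1.21 SD above the mean and a floor of 0 lies 69.3/25.4 = 2.73 SD below it. A beta with those moments has skewness -0.71 and median 75.4.

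**Constructed example (not data), n=22.** Take 16 scores evenly spaced from 64 to 80 and 6 from 20 to 50. The mean is 61.9 (below 63.40), the median 68.8 and Shapiro-Wilk p = 0.001. The sign test has 16/22 above the constant, p = 0.026: non-inferior. The t-test gives p = 0.65: not shown.

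**The case against.** The rule is pre-specified in both documents, and the hypothesis tables use a term that can cover a median. If the median was meant for non-normal data, the sign test is valid for it. SAP 6.5 reports mean, median and 95% CI either way, so a conflict would be visible.

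On size, four of the five Arm B sources have SDs of 3.25 to 12.0. Beta shapes at 3.25, 3.75, 11 and 12 give only about 5.0-6.3% (n=22) and 5.4-6.5% (n=44), against 4.9-5.8% for the t-test. The 15.4% needs the one outlying SD and an arm size that puts every subject in one arm. The mixtures are invented; matching the plan's overall SD, as the 5% mixture nearly does (11.4), does not make its shape the plan's. The t-test is itself above 5% under strong left skew.

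All of this stands as a limit on size. It does not remove the mismatch. The tables' wording leaves open a parameter that the objective names as the mean, and a median reading would still lack its own constant. Reporting the mean makes a conflict visible but does not change the decision.

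**Conclusion.** The documents state a mean objective with mean-derived constants and a mean-based power figure, yet allow the primary decision to be made on the median. That follows from the text alone. The inflation is conditional on marked left skew, a true mean near the threshold and more than about 10 to 12 evaluable subjects in the arm. For Arm B it is negligible for a beta shape at SD 11.08 (about 6-7% vs 5-6% at n=22-50). At SD 25.4 it is about 8 vs 6.5% (n=22), 8 vs 6% (n=32) and 12 vs 5.5% (n=50), with 15 vs 6% at the extreme n=44. The score range, cut-off, shape and arm sizes are assumptions.

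Three stronger readings are tempting, and the documents do not support them:

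- *The rule inflates error in general.* At n=10, the only size the plan powers, there is little or no excess except in the assumed 20% mixture, and there is none in Arm A under right skew.
- *Error rates of 13-44% at n=22, or more at n=44, should be expected.* These come from mixture shapes found nowhere in the documents and are illustrations only.
- *The trial's power is really 51.3%.* That figure is for the sign test alone with normal data, and about 95% of normal samples stay with the t-test. At SD 11.08 and n=10 the combined rule has 84.2% power in a one-sided test.

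The point merits correction before the 24-month data are analysed, because a later choice between mean and median would be data-driven.

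**What to change.** In SAP 3.1.1 and 6.6 and protocol 8.1, 8.2 and 11.3.2 (both arms), replace the choice of test with:

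*The primary analysis in each arm is a one-sample t-test of the mean 24-month total ASES score against 38.41 (Arm A) or 63.40 (Arm B), whatever the normality result. Non-inferiority is concluded if the lower one-sided 95% confidence limit of the mean exceeds that value.*

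Also:

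- Correct the Arm A test sentence in protocol 11.3.2, which labels the 38.41 comparison as RSA.
- Exempt the primary endpoint from SAP 4.10.
- Name the mean as the parameter in the hypothesis tables of both documents.
- Reconcile the two-tailed entries in the sample-size tables with the one-sided 5% test.
- Add a bootstrap-t lower one-sided 95% limit for the mean as sensitivity analysis, and report the median and sign test descriptively.

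**Cost.** Wording and one bootstrap run; no extra subjects or data. Two downsides should be stated.

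- The t-test does not restore 5% under strong left skew: it runs at about 7-11% at n=22-44 and 10-14% at n=10 in the mixtures. The bootstrap-t limit gives 4.4 and 4.6% at n=22 and 44 in the 20% mixture, but 11.6% at n=10.
- Power at a true mean of 74.48 with SD 25.4, t-test vs rule, is 39.0 vs 26.8% (n=10), 61.5 vs 55.9% (n=22) and 85.4 vs 89.7% (n=44): gains at the smaller sizes and a loss of about 4 points at the largest. With SD 11.08 it is 86.6 vs 84.2% (n=10) and 99.6 vs 99.0% (n=22), so no loss.

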### 11.3.3. Secondary Endpoints

The incidence of device-related AEs and implant survivorship will be assessed up to ten years after the index procedure and monitored through collection and analyses. These analyses will be part of the annual and final reports.

Furthermore, time to (earliest) device-related AEs will be analyzed as well. For analysis of the time to the (earliest) device-related AEs as well as the time to secondary procedure (revision, removal, reoperation), the Kaplan-Meier method will be used. The time between surgery and the last available assessment will be used together with the time between date of surgery and the date of secondary procedure. Considered variables, the level of measurement and the planned analysis steps are listed in detail in the SAP.

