### 13.3. RELATIONSHIP TO THE DEVICE

Only events considered possibly, probably or definitely related to the device will be captured for this clinical investigation.

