### 13.5. FORESEEABLE ADEs, SADEs and INCIDENTS

ADEs, SADEs and incidents which may be expected as part of the surgical intervention include:

- *Perioperative complications*
  - Malpositioning of the humeral or glenoidal component
  - Oversizing of implant components
  - Undersizing of implant components
  - Intraoperative fracture of the humerus or glenoid
  - Cement leakage, if applicable
  - Insufficient reduction of the greater or lesser tuberosities
  - Nerve injury, mild (minor motor or sensory loss, or spontaneous recovery)
  - Nerve injury, severe (significant motor or sensory loss or requiring surgical revision)
  - Vessel injury
  - Tendon injury
  - Wound complications (e.g. hematoma, wound healing disturbances)
  - Superficial infection
  - Deep infection
  - Deep vein thrombosis
  - Pulmonary embolism
- *Complications in the follow-up period*
  - Implant dislocation
  - Other subluxation or instability, symptomatic
  - Implant component dissociation, humeral cup from humeral stem
  - Implant component dissociation, humeral head from humeral stem
  - Implant component dissociation, humeral insert from humeral cup
  - Implant component dissociation, glenosphere from baseplate
  - Implant fretting or crevice corrosion
  - Implant breakage/wear, humeral or glenoidal
  - Implant loosening, humeral or glenoidal
  - Implant loosening, humeral or glenoidal with or without screw breakage
  - Radiographic lucency, humeral or glenoidal
  - Rotator cuff tear
  - Pain related to the implant, severe
  - Late infection (e.g. hematogenous or protracted)
  - Periprosthetic fracture of the humerus or glenoid
  - Secondary displacement of the greater or lesser tuberosities
  - Stiffness
  - Stress fracture of the acromion or the scapular neck
  - Stress fracture of the coracoid
  - Scapular notching, asymptomatic or symptomatic

- Suture granuloma
- Heterotopic ossification, asymptomatic or symptomatic
- Healing disturbances of subscapularis tenotomy, if applicable
- Non-union of lesser tuberosity osteotomy, if applicable
- Non-union of primary fracture
- Malunion of lesser tuberosity osteotomy, if applicable
- Malunion of primary fracture
- Wound complications (e.g. hematoma, wound healing disturbances)
- Superficial infection
- Deep infection
- Deep vein thrombosis
- Pulmonary embolism

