6.1. HARMS AND SAFETY

Categorization and definitions of (Serious-, Unanticipated-) Adverse Device Effects, (Serious-) Incidents are given in the CIP.

Evaluation Variable / Question	Level of Measurement	Analysis Plan	Inclusion		
Adverse Events / Incidents			IR	FR	N/A
Perioperative/Postoperative AE (Variable(s): PERPOST)	Qualitative, nominal	Proportions, frequencies, column and row totals, missing proportion (if any).	X	X	
Device-Related Adverse Event / Incident (Variable(s): AEEVENT; AEOTHER)	Qualitative, nominal	Proportions, frequencies, column and row totals, missing proportion (if any). Listing of other Events/Incidents.	X	X	
Describe the AE/Incident (Variable(s): AEDESCRP)	Qualitative, nominal	Listing of other Events/Incidents Description.			X
Unanticipated Adverse Device Event? (Variable(s): AEUADE)	Qualitative, nominal	Proportions, frequencies, column and row totals, missing proportion (if any).	X	X	
Severity (Variable(s): AESEVER)	Qualitative, nominal	Proportions, frequencies, column and row totals, missing proportion (if any).	X	X	
Action Taken (Variable(s): ACTNONE; ACTMEDS; ACTSURG; ACTSHORT;	Qualitative, nominal	Proportions, frequencies, column and row totals, missing proportion (if any).			X

ACTPROHS; ACTOTHER; ACTOTHSP)		Listing of given Other specifications.			
AE Resolution (Variable(s): AERESOLV)	Qualitative, nominal	Proportions, frequencies, column and row totals, missing proportion (if any).			X
Outcome (Variable(s): AEONWOTR; AEONWTTR; AEREWOTR; AEREWTTR; AETEDISB; AEPERMD; AESUEXP)	Qualitative, nominal	Proportions, frequencies, column and row totals, missing proportion (if any).			X
Creation of variable Number of Adverse Device Effects by Site (Variable(s): AEEVENT; SITENUM)	Qualitative, nominal	Proportions, frequencies, column and row totals, missing proportion (if any).	X	X	
Creation of variable Number of Adverse Device Effects per Subject and Site (Variable(s): AEEVENT; SITENUM; SUBID)	Qualitative, nominal	Proportions, frequencies, column and row totals, missing proportion (if any).	X	X	

Table 6.1.1: Adverse Events / Incidents Tables List

Evaluation Variable / Question	Level of Measurement	Analysis Plan	Inclusion		
			IR	FR	N/A
Reoperation					

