Create new variable “Combined Time – First Device Related Adverse Event” (Variable(s): AEONSTDT)	Quantitative, ratio	- Use time between surgery and “most recent” visit for surviving subjects - Use time between surgery and first device related adverse event for subjects with device related adverse event		X	
Use variables “Combined Time – First Device Related Adverse Event” and “Grouping variable – First Device Related Adverse Event”	Qualitative, nominal Quantitative, ratio	Case summary with number and percentage of valid cases/values, missing cases/values (if any) and total cases/values. Kaplan-Meier survival analysis: subject ID, time, status, cumulative proportion, Kaplan-Meier estimate, standard error of KM estimate, number of cumulative events, number of remaining cases, mean for survival time with 95% confidence interval, survival graph, hazard graph.		X	

Table 6.6.2: Endpoints – Secondary Endpoint Time to (earliest) Device Related Adverse Event / Incident Tables List

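### The one curve for device-related events stops at each subject's first event of any severity, and no censoring-adjusted analysis isolates severe events, implant failure or revision/removal

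*SAP*

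**What the plan says.** Protocol 11.3.3 announces that "time to (earliest) device-related AEs will be analyzed as well", and SAP 3.1.2 repeats this. SAP Table 6.6.2 implements it with "events = first (earliest) Device Related Adverse Event". The time variable is built in two parts:

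- Subjects with an event: "Use time between surgery and first device related adverse event for subjects with device related adverse event".
- All others: "Use time between surgery and “most recent” visit for surviving subjects".

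No type, grade or seriousness limits the event. Protocol 13.3 sets the only filter: "Only events considered possibly, probably or definitely related to the device will be captured for this clinical investigation". Protocol 13.5 lists "Scapular notching, asymptomatic or symptomatic", "Heterotopic ossification, asymptomatic or symptomatic", radiographic lucency and wound complications among the foreseeable events, beside implant breakage, dissociation, loosening and deep infection.

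Other outputs bear on the same question:

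- SAP Table 6.1.1 gives frequencies by event type (AEEVENT) and by severity (AESEVER).
- SAP Table 6.1.2 gives reoperations by procedure and by reason.
- SAP Table 6.5.4 gives radiographic findings at each follow-up visit.
- SAP 6.7.3 has a Kaplan-Meier curve for the first reoperation. Protocol 14 counts irrigation and debridement as a reoperation, as well as revision and removal.

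Protocol 8.3 names implant survivorship as a secondary endpoint, assessed up to 10 years.

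**The concern.** A first-event composite answers one question: how long until anything device-related is recorded. A subject with a possibly device-related hematoma in week 1 is an event in week 1, and a component dissociation in year 6 in that subject is not used. Table 6.6.2 also calls event-free subjects survivors, so the curve could be taken for device survival.

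Ten years of follow-up are justified mainly by what happens to the implant late on. If the only time-based outputs mix minor with serious events, or wound procedures with revisions, the report cannot state a 10-year risk of implant failure or revision that allows for incomplete follow-up. The plan expects 56% drop-out (SAP 3.2), so crude proportions are a poor substitute.

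**Working it through.** The documents state no expected rate or precision for this curve, so there is no plan figure to reproduce. The rates below are assumptions.

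**Structure: what each planned output can show**

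| Output | Time axis, censoring handled | Isolates severe events, failure or revision/removal |
|---|---|---|
| Table 6.6.2 curve | yes | no: first device-related AE of any type |
| 6.7.3 curve | yes | no: first reoperation of any type |
| Tables 6.1.1 and 6.1.2 | no | yes, as crude frequencies |
| Table 6.5.4 | by visit only | radiographic failures, among subjects imaged |

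No row has both properties.

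**Size: inputs.** M is the 10-year share of subjects with a minor (non-failure) device-related AE. F is the 10-year share with implant failure. The two are taken as independent.

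**Movement of the curve.** Its 10-year value is 1 − (1 − M)(1 − F), whatever the timing of the minor events. Any change in F therefore moves it by (1 − M) times the failure-only change.

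With M = 30% and a failure hazard of 1% per year, doubled to 2%:

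- Failure-only: 1 − e^(−0.1) = 9.5% to 1 − e^(−0.2) = 18.1%, or +8.6 points.
- Planned curve: 1 − 0.7·e^(−0.1) = 36.7% to 1 − 0.7·e^(−0.2) = 42.7%, or +6.0 points.
- Check: 0.7 × 8.6 = 6.0.

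**Precision.** Assume 50 subjects per arm (the split is not fixed) and ignore drop-out.

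- Planned curve: standard error √(0.367 × 0.633 / 50) = 6.8 points, so the shift is 6.0 / 6.8 ≈ 0.9 standard errors.
- Failure-only: standard error √(0.095 × 0.905 / 50) = 4.2 points, so the shift is 8.6 / 4.2 ≈ 2.1 standard errors.

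Much of the lost sensitivity thus comes from the higher background and its variance. Hidden failures are only part of it.

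**Hidden failures.** With constant hazards, the minor-event hazard over 10 years is −ln(0.7) = 0.357 and the failure hazard is 0.1. The share whose first event is a failure is 0.1 / 0.457 × (1 − e^(−0.457)) = 8.0%, so 1 − 8.0 / 9.5 ≈ 16% of failures are hidden.

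If all minor events fall uniformly in year 1, the hidden share is 0.3 × [(1 − e^(−0.01)) / 0.01 − e^(−0.1)] / 0.0952 = 0.3 × 0.0902 / 0.0952 ≈ 28%.

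**Range over M and F (failure hazard doubled, constant hazards)**

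| M | F | Planned curve | Change | Failure-only change | Hidden |
|---|---|---|---|---|---|
| 10% | 10% | 19.0% to 27.1% | +8.1 | +9.0 | 5% |
| 20% | 10% | 28.0% to 35.2% | +7.2 | +9.0 | 10% |
| 30% | 5% | 33.5% to 36.8% | +3.3 | +4.8 | 16% |
| 50% | 10% | 55.0% to 59.5% | +4.5 | +9.0 | 27% |
| 50% | 5% | 52.5% to 54.9% | +2.4 | +4.8 | 28% |

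**Detection with drop-out.** Simulation used 1,500 trials per setting, with exponential drop-out reaching 56% at 10 years. The figure is the chance that the 10-year estimate under the doubled hazard exceeds the 95th percentile of estimates under the original hazard.

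| M, F | n = 100: planned vs failure-only | n = 50: planned vs failure-only |
|---|---|---|
| 20%, 10% | 37% vs 70% | 21% vs 43% |
| 30%, 5% | 15% vs 45% | 12% vs 32% |
| 50%, 5% | 9% vs 44% | 10% vs 30% |

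**The case against.** The SAP implements what the protocol specifies, so there is no contradiction between the documents. Late failures are not lost from the plan: Tables 6.1.1 and 6.1.2 count them by type, severity and reason, and Table 6.5.4 shows dissociation, breakage, loosening, dislocation and periprosthetic fracture visit by visit, whatever happened earlier. All of this stands. It does not supply a censoring-adjusted risk, and imaging follows each institution's standard of care (Protocol 10.4), so the per-visit tables may have gaps.

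The reoperation curve might be read as the survivorship analysis, since Table 6.7.3 is captioned as revision surgery. Its rule, however, takes the earliest reoperation without restriction by procedure.

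The gain is also limited. With 50 per arm, a 1% yearly hazard and 56% drop-out spread over 10 years, about 50 × (0.01 / 0.0921) × (1 − e^(−0.921)) ≈ 3 failures per arm would be seen. That is a fair reason to keep any added curve descriptive.

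Three stronger readings are tempting and not supported:

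- That the curve stops at any AE at all. Protocol 13.3 restricts capture to events at least possibly device-related.
- That a doubled failure rate would barely move it. This depends on M and F, which the documents do not give. At M of 10–20% with F = 10%, the curve still moves 7 to 8 points.
- That early minor events dominate it. Protocol 13.5 lists notching, heterotopic ossification and lucency under the follow-up period, so putting every minor event in year 1 is an unfavourable case, not the expected one.

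**Conclusion.** The point holds as a gap in the secondary analyses. From the documents alone, no planned analysis that handles censoring isolates severe device events, implant failure, or revision/removal, although implant survivorship to 10 years is a named endpoint.

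The loss of sensitivity is a matter of degree: the planned curve keeps a fraction (1 − M) of the failure signal and carries more background variance. The numerical size rests on assumed M and F, independence of minor events and failures, and an assumed 50 per arm where that is used. The primary ASES test is unaffected. It would be wrong to conclude that the plan cannot see late failures; it sees them only as crude or per-visit counts, or mixed with other reoperations.

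**What to change.** Keep the Table 6.6.2 curve and state beside it that it is not a device-survival curve. Add three time-to-first analyses, by arm:

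1. First device-related AE with AESEVER of Severe, Life-Threatening or Fatal.
2. First implant failure, by a definition on AEEVENT. The documents contain none, so the sponsor should fix and date it before the event data are reviewed for this purpose.
3. First revision or removal of a study component, from the procedure fields of the reoperation form, labelled as the implant-survivorship analysis.

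In each, earlier events outside the definition do not end follow-up. Death is handled as a competing event (in the first analysis, a death that is itself a device-related AE counts as an event), and results are given as cumulative incidence with confidence intervals and numbers at risk.

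Event type, severity, onset date, reoperation procedure and date of death are already in the SAP's variables or derived times. The cost is SAP wording and three further runs, plus a check that the software used gives a competing-event estimate. The downside is more output with few events per curve, so these analyses should be called descriptive and carry no tests.
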